Outcome measures	Primary outcome measures will be beliefs, perceptions of patients and healthcare professionals regarding the MRI diagnosis in respect to patient's improvement and the psychosocial impairments associated with MRI report. Secondary outcome measures will be the influence of these psychosocial impairments on patients' response to physiotherapy.
Analysis methods	Qualitative part of the study will utilize FG or one to one interview method of data collection, the audio recorded interview will be transcribed verbatim then thematically analysed. The quantitative part of the study will utilize questionnaires for data collection, which will be analysed by Statistical Package for the Social Sciences software program.

ABBREVIATIONS

AE	Adverse event
CI	Chief Investigator
CRF	Case report form
CLBP	Chronic low back pain
GCP	Good Clinical Practice

LBP Low back pain

NS-CLBP Non-specific chronic low back pain

REC Research ethics committee
UoN University of Nottingham
MRI Magnetic resonance imaging
RCT Randomised Control Trial

Table of Contents

STUDY PERSONNEL AND CONTACT DETAILS	2
SYNOPSIS	3
ABBREVIATIONS	5
STUDY BACKGROUND INFORMATION AND RATIONALE	
The role of post-procedural information	
The role of psychological factors and the chronicity	
The Saudi Arabian context	10
STUDY OBJECTIVES AND PURPOSE	11
PURPOSE	
PRIMARY OBJECTIVE	
Qualitative study:	
Quantitative Study:	
Process evaluation:	
STUDY DESIGN	
STUDY CONFIGURATION	
STUDY MANAGEMENT	
DURATION OF THE STUDY AND PARTICIPANT INVOLVEMENT	
End of the Study	
ETHICAL APPROVAL	
SELECTION AND WITHDRAWAL OF PARTICIPANTS	
Recruitment	
For the focus groups and interviews:	
Inclusion criteria:	
Exclusion criteria:	
For the feasibility RCT:	
Inclusion criteria:	
Exclusion criteria:	
Participant withdrawal	
Informed consent	
STUDY REGIMEN	
Compliance	
Criteria for terminating the study	
DATA ANALYSES	
Methods	_
Sample size and justification	
ADVERSE EVENTS	19
PROCESS EVALUATION	19
ETHICAL AND REGULATORY ASPECTS	20
ETHICS COMMITTEE AND REGULATORY APPROVALS	
INFORMED CONSENT AND PARTICIPANT INFORMATION	
RECORDS	
Case Report Forms	
Source documents	
Direct access to source data/documents	
DATA PROTECTION	22

QUALITY ASSURANCE & AUDIT	2 3
INSURANCE AND INDEMNITY	2 3
STUDY CONDUCT	
STUDY DATA	
RECORD RETENTION AND ARCHIVING	
DISCONTINUATION OF THE STUDY BY THE SPONSOR	
STATEMENT OF CONFIDENTIALITY	
PUBLICATION AND DISSEMINATION POLICY	24
STUDY FINANCES	24
Funding source	24
Participant stipends and payments	24

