cortical representation of neuron firing in chronic pain patients how found that these patients display

more neurons firing in the memory area when they asked to imagine doing daily activities whereas

control group showed more firing in the motor areas. Chronic back pain patients tend to display a

heightened fear of movement (kinesiophobia) and increased depression (George and Beneciuk, 2015).

The Saudi Arabian context

The healthcare system in Saudi Arabia is government-funded and publically available to all; 79% of

all patients receive treatment in the public system while the remainder are treated privately (Almalki et

al., 2011). Insurance companies cover the majority of private patients. The public healthcare system is

structured into three levels: primary, secondary and tertiary. Advanced radiological investigations are

not available at the primary level.

CLBP patients in Saudi Arabia have the option of directly seeking medical treatment in the private

system, thus bypassing the primary triage level. A study performed in a 440-bed university hospital in

the eastern region of Saudi Arabia showed that the average number of MRI assessments performed

annually was 2725, with the highest proportion attributed to adult orthopaedic and spine referrals;

these figures have increased yearly since 2007 (Jabali et al, 2015). This hospital is considered small in

comparison to the referenced medical cities in the region, which serve 1200 beds. Nonetheless,

university hospital practitioners could be expected to have a good awareness of the literature and

guidelines.

McCullough et al. (2012) demonstrated that lower back pain patients who receive MRI reports without

also receiving information of the likelihood of false positive results were more likely to be prescribed

pain medication than those who had received information on asymptomatic prevalence. The increased

prescription of medication was associated with increased symptoms. With the knowledge that

psychological factors have a significant influence in NS-CLBP, and that MRI results can instigate a

Page 10 of 28

change in symptoms as well, it will be interesting to determine whether pain is preceded by

psychological changes.

STUDY OBJECTIVES AND PURPOSE

PURPOSE

This study aims to identify the psychosocial factors associated with MRI diagnosis in patients with

non-specific low back pain. It will explore the experience of this group of patients in Saudi Arabia and

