The data from these focus groups or interviews will be analysed thematically to assist in identifying

the main psychosocial factors associated with diagnosing NS-CLBP patients using an MRI diagnosis.

Part II: Outcome measures will be selected according to the emerging themes from Part I.

Patients who meet the inclusion criteria will be randomly allocated to have an MRI scan

followed by physiotherapy or receive physiotherapy alone. A booklet of outcome measures

will be completed following consent and prior to randomization before physiotherapy and

repeated after physiotherapy treatment. Part II will be held in King Fahad Medical City.

Healthcare practitioners and patients with chronic low back pain and factors affecting trial

delivery will conduct process evaluation alongside the feasibility study to explore the

acceptance of randomisation.

STUDY MANAGEMENT

The chief investigator (CI), under the supervision of [name] and [name], will

be responsible for the management and progression of the study.

The methods of data collection are focus groups or interviews and questionnaires. In Part, FG, the

interviews or I will be audio recorded, after obtaining permission from each participant. The FG

usually takes 90 minutes for each group and they will be held at King Fahad Medical City. The CI will

contact candidate participants by telephone to arrange the time of the interview. After each FG or

interview, the audio recording will be evaluated to ensure that a good quality recording was obtained.

Then, the audio recording will be transcribed in verbatim and checked against the original audio

recording. Finally, the transcripts and the audio recording will be stored in a computer hard drive with

password protection.

In Part, II of the study, the themes that emerged from the interviews will be used to create a

booklet of outcome measures. The handbook will contain outcome measures of psychosocial

impairments with strong psychometric properties as well as modified questions, which are not

Page 13 of 28

The Psychosocial Impact of MRI Diagnosis in Chronic Non-Specific Low Back Pain

Study ID/ Psychosocial -Factors

covered by the outcome measure questionnaires. The time needed to fill in the booklet should

not exceed 20 minutes. This booklet of measures will be given to two groups of patients. The

first group will be patients who have had an MRI diagnosis for their back pain in the last

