month and the second group will be those who have not had an MRI scan. The outcome

measures booklet will be completed before starting and after finishing the physiotherapy

treatment.

The CI is responsible for all of the study management and is the data custodian as well.

DURATION OF THE STUDY AND PARTICIPANT INVOLVEMENT

The duration of the study will be approximately 28 to 36 weeks. Part I will require 12 to 16 weeks to

conduct the three focus group interviews, which will require additional time to arrange to

accommodate the professionals' busy schedules. Part II of the study will run for 16 to 20 weeks.

Additional process data collection will take place parallel to Part II and. Overall, the two parts of the

data collection will require 32 to 40 weeks.

End of the Study

The study will end after completing the last participant interview during the process evaluation.

ETHICAL APPROVAL

Ethical approval for this study will be sought from the Faculty of Medicine & Health Sciences

Research Ethics Committee (REC) and the local Ethics Committee at the hospital in Riyadh. Ethics

approval will also be sought from each hospital participating in this study.

Page 14 of 28

SELECTION AND WITHDRAWAL OF PARTICIPANTS

Recruitment

Part I: INTERVIEW STUDY

Recruitment of patient participants: [name] will obtain the ethical permission to

conduct the study from King Fahad Medical City. The physiotherapy team leader will invite the

patients who meet the inclusion criteria to a FG interview. Recruitment will take place in the

physiotherapy department. A consent form and patient information sheet will be given to the patients.

[name] will be responsible to answer any question participants may have before

signing the consent. A signature is required from each patient to document his/her acceptance to enrol

in the study. There will be six to eight patients, male and female without restriction in sex

representation.

Recruitment of clinician participants: [name] will obtain the ethical permission to

conduct the study from King Fahad Medical City. Physiotherapists and doctors who meet the inclusion

criteria will be invited to participate in a focus group. Physiotherapists and doctors will be invited by

the team lead. An ethical consent form and a participant information sheet will be given to the

participants. A signature is required from each participant to document his/her acceptance to enrol in

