the study. Each group will contain six to eight clinicians, male and female. If FG is not possible,

especially with physician, then one to one interview will be performed.

Part II:

In Part II of the study, [name] will approach the administrators at King Fahad Medical

City for approval to conduct the second part of the study. The lead physician will invite all patients

who met the inclusion criteria to take part in the study using the patients register program. An ethical

consent form and an information sheet will be handed to the patients. [name] will be

responsible to answer any question participants may have before signing the consent. A signature is

required from each patient to document his/her acceptance to enrol in the study. To ensure equal

distribution between groups, block randomization schedule will be used to assign patient into groups;

MRI group and control group. The MRI group will have MRI scan and discuss the result with their

doctors before having the physiotherapy treatment. The control group will have physiotherapy

treatment without MRI scan.

Process Evaluation:

Patient particepent of Part II, will be invited by email to participate in process evaluation interviews.

Additional consent forms and information sheets related to this study will be emailed to participants.

Reply from the participant with the approval is required t to document his/her acceptance to enrol in

the study. [name] will be responsible to answer any questions concerning these

documents.

The research team in King Fahad Medical City, including doctors and physiotherapists, will be invited

by email to participate in interview study to evaluate their experiences of the feasibility RCT. Mr

[name] will be responsible for contacting the research team and explaining the study aims.

For the focus groups and interviews:

Inclusion criteria:

Patient participants:

Male and female aged 18 to 65 years, CLBP with no clear medical diagnosis who had an MRI scan

and a report for LBP in the last month (e.g., malignancy, fracture, infection, spinal stenosis,

sponylosthesis or inflammatory disease). Chronicity will be considered if the pain has persisted for

more than three months.

Clinician participants:

Page 16 of 28

Physicians in direct contact with people with NS-LBP and with the authority to refer patients for MRI

will be recruited as clinician participants. Inclusion criteria for physiotherapists include outpatient

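### The protocol places the first booklet before randomisation in one section and after the MRI in another, and no clear version measures patients both before MRI and between disclosure and physiotherapy

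*Protocol*

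**What the plan says.** **First booklet, Study configuration (Part II).** The booklet "will be completed following consent and prior to randomization before physiotherapy and" is then "repeated after physiotherapy treatment. Part II will be held in King Fahad Medical City". On its plainest reading this gives two time points: one after consent and before randomisation, one after physiotherapy.

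**First booklet, Study management.** The same booklet goes to two groups. One is already scanned, within a period given as one month: "first group will be patients who have had an MRI diagnosis for their back pain in the last". The other group is unscanned. As to timing, the text reads: "measures booklet will be completed before starting and after finishing the physiotherapy". Randomisation is not mentioned, and one group has already been scanned when it receives the booklet.

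**Order of events, Recruitment (Part II).** Patients are assigned by block randomisation to one of two arms: "MRI group and control group. The MRI group will have MRI scan and discuss the result with their". That consultation comes ahead of physiotherapy. Control patients go to physiotherapy and are not scanned.

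**Eligibility, inclusion criteria for the feasibility RCT.** As written, every entrant must have had an MRI and a report for low back pain within the past month.

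**What the booklet is for.** The Synopsis states: "Secondary outcome measures will be the influence of these psychosocial impairments on patients' response to physiotherapy". The Part II objectives are feasibility of randomising, recruitment rate, integrity of the protocol and the sample size of the definitive trial. No section gives a number of sessions, a course length, a waiting time for MRI, or a follow-up week counted from randomisation.

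**The concern.** The intervention under study is having an MRI and being told the result. A baseline has to come before that, in both arms. If staff follow Study management, the MRI arm's first booklet may already contain the reaction to the result while the control arm's does not, and the two would not be comparable as baselines. Staff could also follow a mixture of the two sections, patient by patient.

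The secondary outcome links impairments arising from MRI to the later response to physiotherapy. That calls for a psychosocial measurement after disclosure and before physiotherapy, and for a pre-MRI value if the change due to MRI is to be seen within patients. Neither section clearly provides both.

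Finally, a follow-up fixed only to the end of physiotherapy lets time since randomisation differ by arm, because only one arm has a scan and a consultation to get through first. The standard deviation and the baseline to follow-up correlation that would inform the definitive sample size depend on both timings.

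**Working it through.** The protocol states no figure here that can be reproduced, so the check sets the sections side by side.

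**1. Sequences, taking the order of events from Recruitment (Part II)**

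| Version | MRI arm | Control arm |
|---|---|---|
| Study configuration | booklet, randomisation, MRI, discussion, physiotherapy, booklet | booklet, randomisation, physiotherapy, booklet |
| Study management | MRI, booklet, physiotherapy, booklet | booklet, physiotherapy, booklet |

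The first version has a clean pre-MRI baseline and nothing between disclosure and physiotherapy. The second has a booklet between MRI and physiotherapy and no pre-MRI baseline.

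**2. Where the conflict lies.** Completing a booklet before physiotherapy is compatible with completing it before randomisation, since both can be true of one booklet. The conflict comes from Study management's description of a group already diagnosed by MRI. The inclusion criterion adds a third account: read literally, both arms enter with a recent MRI. Then even a pre-randomisation booklet follows an MRI, and no control patient fits Study management's unscanned group.

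**3. What each version can estimate.** Let *d* be the mean shift in a score from disclosure, present just before physiotherapy, and *T* the mean difference between arms at the final booklet. Leave unequal timing aside for now.

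- Study configuration: baselines are equal in expectation, so the arms differ by *T* at the end, whether analysed as final score, change or baseline-adjusted score. *T* is the total effect of adding MRI. *d* is not observed.
- Study management, with assignment by randomisation: the arms differ by *d* at the first booklet and by *T* at the last. Change from the first booklet gives *T* − *d*. Adjusting for it with slope *b* gives *T* − *b* × *d*.
  - If the shift persists fully (*T* = *d*), the change score gives *d* − *d* = 0.
  - If it fades fully (*T* = 0), the change score gives 0 − *d* = −*d*.
  - An unadjusted comparison of final scores still gives *T*, and one of first scores gives *d*.

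The damage under Study management therefore arises when the first booklet is treated as a baseline.

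**4. Timing of the final booklet.** Let *w* be the extra wait in the MRI arm for scan and discussion, and *L* the length of physiotherapy, taken as equal in both arms. With other delays equal, control is assessed at *L* after randomisation and the MRI arm at *L* + *w*, a difference of *w*. Neither is stated. The only bound available comes from Part II lasting 16 to 20 weeks (Duration of the study) and recruitment lasting 6 weeks (Sample size and justification). The last recruit has at most 16 − 6 = 10 to 20 − 6 = 14 weeks for everything.

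As an illustration only, assume *L* = 6 weeks and *w* = 2 to 6 weeks. The MRI arm is then assessed at 6 + 2 = 8 to 6 + 6 = 12 weeks, against 6 for control. The upper case would not fit the 10 weeks left under a 16-week Part II.

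**5. Cost of one further booklet.** Study management caps completion at 20 minutes: 20 × 30 patients = 600 minutes = 10 hours.

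**The case against.** The strongest defence is that Part II is a feasibility trial with 15 patients per arm. No efficacy conclusion rests on the schedule, and both arms receive physiotherapy, so a pre-randomisation baseline leaves a valid randomised comparison. This stands and limits the severity. It does not remove the point, because protocol integrity and the definitive sample size are stated objectives, and an analysis plan cannot supply a booklet that was never collected.

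The Study configuration wording is also unpunctuated and could be stretched to three time points: before randomisation, before physiotherapy and after it. That is possible, but it is not clear enough to run a site on.

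Four stronger readings are tempting and not supported:

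- A reader might infer that no version has a booklet between disclosure and physiotherapy, so that the psychosocial state and the response are always first measured together. That is true only of Study configuration.
- A reader might infer that the effect of MRI cannot be isolated. Under Study configuration the total effect can be estimated, subject to timing. What is lost is the immediate effect of disclosure.
- A reader might infer that none of the effect is recovered. That needs a change score together with full persistence, or the immediate shift as target together with full fading. The protocol fixes no such analysis.
- A reader might treat the order of psychological change and pain as a trial objective. The text, "change in symptoms as well, it will be interesting to determine whether pain is preceded by" psychological changes, is a background remark under The Saudi Arabian context and is absent from the listed objectives.

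**Conclusion.** The protocol gives incompatible accounts of the first booklet. Following Study management makes the MRI arm's baseline post-intervention, and the inclusion criterion deepens the conflict. No clear version has both a pre-MRI baseline and a measurement after disclosure but before physiotherapy. With the pre-randomisation baseline the total effect of adding MRI remains estimable, while the immediate effect of disclosure and its influence on response to physiotherapy cannot be separated.

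For equal course lengths the MRI arm is assessed later after randomisation. The direction follows from the stated order of events; the size cannot be derived from the protocol. The distortion from a post-MRI baseline is likewise conditional, on a real shift at disclosure and on the first booklet being used as the baseline.

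Severity is moderate: the trial is small and aimed at feasibility, but its data inform the definitive sample size.

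**What to change.** 1. Reconcile Study configuration, Study management and the RCT inclusion criteria on one booklet after consent and before randomisation in both arms, and name it as the baseline. State whether a recent MRI before entry is intended, since as written that criterion conflicts with an unscanned control group.
2. Add one booklet just before the first physiotherapy session in both arms, which in the MRI arm is after the result has been discussed. Record its date, because it falls later after randomisation in that arm.
3. Set the final booklet at one fixed time from randomisation, the same in both arms. Record the dates of MRI, discussion, and first and last physiotherapy session.

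The first change costs only wording. The second costs at most 20 minutes per patient, about 10 patient-hours for 30 patients. The third replaces unequal time since randomisation with unequal time since the end of physiotherapy, which the recorded dates would allow the team to describe.

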Study Configuration	Mixed methods study with part one encompassing three qualitative focus group (FG) or interviews followed by a quantitative feasibility randomized control trial (RCT) with concurrent process evaluation.
Setting	Multicentre, Primary and secondary care services in Riyadh, Saudi Arabia.
Sample size estimate and Study Participants	Focus groups or interviews using purposeful sampling will comprise of 6–8 people with chronic non-specific low back pain, 6–8 physiotherapists and 6–8 orthopaedic surgeons (part I); 30 patients with chronic low back pain for the feasibility RCT (part II). There will be 38 to 44 study participants overall for part I and II. Process evaluation will include interviews with 4-6 patients and 2-4 healthcare practitioners.
Eligibility criteria	Part I: Participants with history for three months chronic non-specific low back pain whom are diagnosed with MRI from King Fahad Medical City. For the healthcare professionals, physiotherapists and orthopaedic surgeons who have experience in managing people with chronic low back pain in addition to having a privilege to request MRI for doctors. Part II: Participants over the age of 18 and below 65, of any gender, who have been diagnosed with chronic low back pain for more than 3 months
Description of Procedure	and didn't had physiotherapy treatment in the past 6 months. Part I: using FG method or interview, three FGs will be conducted with patients with chronic non-specific low back pain, orthopaedic surgeons and physiotherapists from King Fahad Medical City, Saudi Arabia. If FGs is not applicable, one- to-one interview will be conducted This will take place for approximately four months, following this study; the main psychosocial factors associated with MRI diagnosis will be identified. Part II: the psychosocial factors will be assessed on two randomized groups of patients; those who receive physiotherapy alone and those who had an MRI scan proceeding physiotherapy treatment. Following the trial, further interviews will be conducted with staff (Surgeons and physiotherapists and recruiting staff) in each site in the form of 'end of site meetings' to explore factors affecting recruiting and trial procedures.
Duration of study	Approximately 28 to 36 weeks. For part I, FG or interviews will run for 12 to 16 weeks. Part II, will require 16-20 weeks.

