physiotherapists with a primary interest in LBP management.

Exclusion criteria:

Women who are pregnant or less than six months postpartum, or have received pain-relieving

procedures (injection or denervation) in the previous three months or have evidence of neurological

impairment will be excluded from the study.

For the feasibility RCT:

Inclusion criteria:

Male or female aged 18 to 65 years; CLBP with no clear medical diagnosis who had an MRI scan and

a report for LBP in the last month (e.g., malignancy, fracture, infection, spinal stenosis, sponylosthesis

or inflammatory disease) will be included. Chronicity will be considered if the pain has persisted for

more than three months. Patients must not have had physiotherapy treatment in the six months prior to

the study.

Exclusion criteria:

Women who are pregnant or less than six months postpartum, or have received pain-relieving

procedures (injection or denervation) in the previous three months or have evidence of neurological

impairment will be excluded from the study.

Participant withdrawal

Participation in this study is voluntary. All participants are free to withdraw from the study at any

time, without fear of penalty of impact on their healthcare and the researcher could remove

participants from the study if needed as well. If there is a withdrawal from the study, the information

collected prior to the withdrawal will not be removed and shall be used in the analysis. The treatment

given to the patients will not be affected by their withdrawal from the study. Patients who drop out of

the study will not be replaced.

Page 17 of 28

The Psychosocial Impact of MRI Diagnosis in Chronic Non-Specific Low Back Pain

Study ID/ Psychosocial -Factors

Informed consent

The consent form must be signed and dated prior to participating in the study. The CI will explain the

study by providing an information sheet and answering the questions of the patients and clinicians.

Both healthcare practitioners and patients will be contacted during and after the feasibility trial asking

if they would be willing to take part in an interview at the end of the trial, about their experiences of

taking part in the trial, the process of the trial and factors affecting its delivery.

STUDY REGIMEN

Compliance

Participation in the FG and the returned handbook of outcome measures are the indictors for

compliance.

Criteria for terminating the study

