Dissolution of the study is unlikely, however if the ethical approval is withdrawn then the

study will be terminated.

DATA ANALYSES

Methods

In Part I of the study, the qualitative part, the FG or interviews will be audio recorded and then

transcribed verbatim to be analysed thematically using Framework analysis (Ward et al., 2013). The

Nvivo software programme will be used later for coding and management.

In Part II of the study, the quantitative part, the Statistical Package for the Social Sciences (SPSS) will

be used for analysis. The process evaluation will require interviews with both healthcare professionals

and trial participants (patients) and analysis of recruitment process documentation completed by the

research team.

Page 18 of 28

All study data will be analysed using the University of Nottingham (UoN) computers and it will be

stored in the UoN server.

Sample size and justification

Part I (FG or interviews): A purposive sampling method will be utilised. In this study, a subgroup of

the populations, healthcare professionals with experience in the management of chronic LBP and

people with chronic LBP, will be identified and then select cases from this subgroup will be

recognised in a purposive manner. Both the patients with chronic LBP and the healthcare professionals

will be intentionally and purposefully chosen according to the inclusion and exclusion criteria defined

earlier.

Part II: since this is a feasibility study a sample size calculation is not required, however a realistic

target of 30 participants estimated based on audit data from recruitment centre, which suggest 80

people with general spine problems are seen in each clinic per month. Assuming two third are not

eligible and further 50% refused consent, we will recruit patients for 6 week from two clinics. The

sample size for each arm of the feasibility RCT will be 15 participants.

Process evaluation interviews will involve 4-6 participants and 2-4 healthcare practitioners.

ADVERSE EVENTS

Since no adverse events (AE) are expected to occur because of participating in the study, no AE data

will be collected. However, since the study will be exploring peoples' experiences, some individuals

may become emotional and uncomfortable with sharing their experiences. If this occurs, the researcher

will stop the discussion and ask that participant if he/she is willing to continue with the discussion.

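### RCT eligibility repeats the interview study's: its recent-MRI requirement conflicts with the no-MRI control arm, and once that is reconciled nothing checks before randomisation that a patient can be scanned

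*Protocol*

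**What the plan says.** All references are to the protocol.

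- **For the feasibility RCT, inclusion criteria:** the sentence opens "Male or female aged 18 to 65 years; CLBP with no clear medical diagnosis who had an MRI scan and" and goes on to require a report from within the last month. Apart from trivial wording and an added condition on recent physiotherapy, it is the inclusion sentence used for interview patients.
- **For the feasibility RCT, exclusion criteria:** a single sentence that opens with pregnancy and the postpartum period and later contains "procedures (injection or denervation) in the previous three months or have evidence of neurological" before ending on impairment. The same sentence stands word for word in the interview section. Pregnancy is the only item that could bear on scanning.
- **Study Configuration, Part II:** "Patients who meet the inclusion criteria will be randomly allocated to have an MRI scan" and then physiotherapy, or physiotherapy alone.
- **Recruitment, Part II:** block randomisation to "MRI group and control group. The MRI group will have MRI scan and discuss the result with their" doctors before physiotherapy; controls have physiotherapy "treatment without MRI scan".
- **Study Management:** the booklet goes to one group with an MRI diagnosis in the last month and a second group who have had no MRI.
- **Synopsis, eligibility criteria:** the RCT population is given as "Participants over the age of 18 and below 65, of any gender, who have been diagnosed with chronic low back pain for more than 3" (the unit being months), with no physiotherapy in the past six months. No earlier MRI is required.
- **Sample size and justification:** the "sample size for each arm of the feasibility RCT will be 15 participants".

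**The concern.** Two parts of the eligibility text do not fit a trial in which MRI is the randomised intervention.

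First, the inclusion criterion admits only patients who already have a recent scan and report. Applied literally, every control would enter with an MRI result in hand, and the contrast would be a further scan against no further scan. That is not the comparison described in Study Configuration, Recruitment, Study Management or the synopsis.

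Second, the exclusion list served interview patients who had, by definition, already been scanned, so it needed no item on whether they could be. In the RCT that question matters, and no visible section asks it before allocation. If the recent-MRI clause is removed or narrowed to match the design, the only barrier to randomising a patient who cannot be scanned goes with it. Such a patient would fail the allocation if assigned to MRI, while nothing would show if the same patient were assigned to control.

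The main quantitative objective is the feasibility of randomising, judged by patients' and physicians' acceptance. Non-receipt in one arm that stems from screening is a different matter from poor acceptance, and the two should be kept apart.

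**Working it through.** **1. Setting the passages side by side**

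| Source | Earlier MRI required? | Ability to have MRI checked? |
|---|---|---|
| RCT inclusion criteria | Yes, within the last month | Only indirectly, through that requirement |
| RCT exclusion criteria | – | No item |
| Synopsis, Part II | No | No item |
| Study Management | First group yes, second group no | No item |
| Recruitment, Part II | Scan follows allocation in the MRI arm; none in control | No item |

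Under the literal RCT inclusion criterion, the number of randomised patients who cannot be scanned is close to zero, because each was scanned within the past month. Under the synopsis eligibility and the design description, it depends on the share of such patients in the clinic.

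**2. Size once the clause is reconciled with the design**

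Inputs: n = 15 in the MRI arm (Sample size and justification); p = share of otherwise eligible patients who cannot be scanned. The documents give no p, so 1–10% is assumed. The calculation takes patients as independent and assumes none is filtered out earlier.

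Expected failures in the MRI arm = 15p. Chance of at least one = 1 − (1 − p)^15.

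| p (assumed) | Expected of 15 | Chance of at least one |
|---|---|---|
| 1% | 0.15 | 1 − 0.99^15 = 14% |
| 2% | 0.30 | 1 − 0.98^15 = 26% |
| 5% | 0.75 | 1 − 0.95^15 = 54% |
| 10% | 1.5 | 1 − 0.90^15 = 79% |

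Failures of this kind in the control arm: 0 at every p. One failure lowers receipt of allocation in the MRI arm by 1/15 = 6.7 percentage points.

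**3. Whether screening would threaten the recruitment target**

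The protocol's inputs are 80 patients per clinic per month, two clinics, 6 weeks, one third eligible and one half of those consenting.

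- 6 weeks taken as 1.5 months: 80 × 2 × 1.5 × 1/3 × 1/2 = 40.
- 6 weeks taken as 1.38 calendar months: 80 × 2 × 1.38 × 1/3 × 1/2 = 36.8.

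Neither equals the stated 30, but both exceed it, so the target is reachable on these inputs. Multiplying by (1 − p):

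- p = 1%: 39.6 or 36.4.
- p = 10%: 36.0 or 33.1.

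The yield after screening is therefore about 33–40, still above 30. If the assumed two-thirds ineligible already covers patients who cannot be scanned, the loss is smaller.

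**The case against.** A reader might infer that the protocol as written already lets patients who cannot be scanned meet every criterion and be randomised. The documents do not support that: the RCT inclusion criterion requires a recent MRI, and someone who cannot have one fails it. The mechanism becomes live only under the synopsis eligibility and the no-MRI control design. The contradiction over the earlier scan is thus the larger defect, and adding an exclusion while leaving that clause untouched would change almost nothing.

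A reader might also infer a safety hazard, or a feasibility result that must be misread. Neither follows. The documents do not say when, or by whom, suitability for MRI is checked before a scan, so a hazard cannot be shown. The protocol records participation, attrition and drop-out, interviews patients and staff about trial delivery, and lists assessment of protocol integrity among its objectives, so a screening problem could well come to light. The rule that drop-outs are not replaced need not apply either: an unscanned patient can still have physiotherapy and return the booklet, which is the stated sign of compliance.

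Some of these patients may also be identified earlier, when the lead physician invites them or when they read the information sheet. The consent pages are not available for this review, so what they say about MRI cannot be judged.

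What stands is the contradiction itself, the identical exclusion sentence, the absence of any visible check before allocation, and the fact that any resulting failure can arise in one arm only.

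**Conclusion.** The point holds in conditional form. The RCT inclusion criterion conflicts with the control arm, the second group in Study Management and the synopsis, and these must be reconciled. If that removes the recent-MRI requirement, the exclusion list leaves a gap through which patients who cannot be scanned could be randomised, with failure of allocation in the MRI arm only.

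The effect is modest: fewer than two patients expected even at the top of the assumed range, and less than one at 5% or below. The range of p is an assumption and drives the result. The reasons to act are that the remedy is cheap and that the inclusion criterion has to be edited anyway. Correcting the inclusion text alone would open the gap, so the two belong in one amendment.

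**What to change.** In one edit of the RCT eligibility section:

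1. Reconcile the inclusion criterion on a recent MRI with the synopsis, Study Management and Recruitment, so that all four describe the same population and the same contrast.
2. Add, for the RCT only, a criterion that the patient must be able to undergo MRI. The investigators define what that covers.
3. Apply it to every patient after consent and before randomisation, whichever arm may follow.
4. Count those who fail as ineligible in the recruitment figures, not as drop-outs or refusals.

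The cost is one added criterion and a short check that is also done for patients who will become controls. A few otherwise eligible patients are lost, but on the protocol's own inputs the expected yield stays above the target of 30.
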